Study Setting and Data Collection	This study will recruit up to 100 General Practices within Primary Health Network (PHN) regions of New South Wales (NSW) and Western Australia (WA). Data collection will be facilitated by CTCs.															
Study Duration	
  
 Timeframe	Activity	
   
 November 2022 - February 2023	Complete co-design and refinement of multicomponent intervention (University of Sydney HREC 2022/755)	
 
 August 2023	Ethics approval (University of Sydney Clinical Trials)	
 
 January – August 2023	Engagement with PHNs and establishment of research agreements	
 
 August 2023	Recruitment of CTCs	
 
 September 2023	General Practice Recruitment	
 
 October 2023	Baseline data collection	
  
		Timeframe	Activity	November 2022 - February 2023	Complete co-design and refinement of multicomponent intervention (University of Sydney HREC 2022/755)	August 2023	Ethics approval (University of Sydney Clinical Trials)	January – August 2023	Engagement with PHNs and establishment of research agreements	August 2023	Recruitment of CTCs	September 2023	General Practice Recruitment	October 2023	Baseline data collection
Timeframe	Activity															
November 2022 - February 2023	Complete co-design and refinement of multicomponent intervention (University of Sydney HREC 2022/755)															
August 2023	Ethics approval (University of Sydney Clinical Trials)															
January – August 2023	Engagement with PHNs and establishment of research agreements															
August 2023	Recruitment of CTCs															
September 2023	General Practice Recruitment															
October 2023	Baseline data collection															

	March - August 2024	Delivery of intervention
	March - August 2024	Implementation support of intervention arm
	March - August 2024	Monitor of control arm (usual care)
	September - October 2024	Post-intervention data collection
	October 2024	Effectiveness evaluation

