6.1. Background and rationale

Colorectal cancer (CRC) is the fourth most common cancer in Australia and screening for precancerous lesions and early stage cancer is proven to decrease CRC mortality and morbidity (1,2). In Australia, the National Bowel Cancer Screening Program (NBCSP) provides a self-administered stool test, the immunochemical faecal occult blood test (iFOBT), mailed to the home of all Australians aged 50-74 years. If an individual has above average risk of CRC (e.g., a family history of the disease), specialised screening regimens via colonoscopy are recommended in place of NBCSP screening (3). Optimising the NBCSP and ensuring people at above average risk are screening appropriately are critical to reducing CRC mortality and morbidity in Australia. The NBCSP alone has the potential to save 84,000 lives by 2040 if participation can reach and be sustained at 60% (4).

The CRC burden in Australia remains high and there are many people who do not screening according to the evidence-based guideline recommendations (3). That is, they either do not screen at all (under-screened) or screen using colonoscopy when they are not at above average risk (inappropriately screened). Under-screened individuals are at higher risk of developing advanced-stage CRC, whereas inappropriately screened individuals can place unnecessary strain on the healthcare system through low-value colonoscopies (5). Improving guideline-appropriate CRC screening will improve CRC outcomes and optimise the use of CRC-specific health services.

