10.2.1. Intervention

The intervention is a multi-component, co-designed general practice-led intervention designed based on the evidence review and co-design process in the MAIL, GP & SCALE project.

A co-design process with GPs and practice staff (University of Sydney HREC 2022/755) assessed the intervention components to determine their practicability, acceptability, and perceived risk within general practice.

The intervention components are evidence-based and available from existing tools and systems. A brief outline of the intervention components is provided in Table 1 and further description in Appendix 6A. Where required, permission to use resources has been or will be sought, and the original sources will be appropriately acknowledged. Practices in both the intervention and control arms will have had some level of exposure to NBCSP related material prior to the intervention. Practices of the intervention arm will be actively supported and encourage to use materials and the evaluation will help determine whether it is the added support that improves the use of the available intervention components.

The intervention components will not change but the specific details may be refined over the trial. For example, GP education is a critical component of the intervention and existing educational webinars, resources and factsheets developed by Cancer Council Australia will be used (27). This component may be modified in future as information relating to the National Bowel Cancer Screening Program (NBCSP) are updated. The research team is aware that the NBCSP is currently undergoing review by the Department of Health and Aged Care that may impact the information provided to GPs and any education may require updating. The fundamental component will not change, and updates will be requested as future modifications for committee reviews.

Table 1 Intervention Components

Intervention component	Target	Description
Decision support tools	GPs and practice nurses	Decision-aids to support GPs/patients determine guideline-appropriate screening pathways.
Electronic point-of-care prompt	GPs	Electronic reminders integrated into CIS
Clinical system enhancement	Whole-of-practice	Use of cancer screening toolkit and clinical audits of patient data to identify under-screened patients and integrate practice CIS with the NCSR

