10.2.2. Implementation strategies

A core component of the CTC's role is to support implementation using these strategies. Evidence-based implementation strategies (listed in Table 2) will be used to support the intervention arm by preparing and supporting the general practices in engaging with the intervention. The strategies have been developed against ERIC refined compilation of strategies (13).

Implementation outcomes, the adoption of in-practice activities and implementation strategies to support CRC screening, are also secondary outcomes of the trial.

Table 2 Implementation strategies

ERIC Strategy (13)	Stage of trial	Target of implementation strategy	Example
Alter incentive/allowance structures	During trial	GPs	Work to incentivise the adoption of intervention components by facilitating Continuing Professional Development points for completion. NB: the CTC will highlight the available opportunity for practices to pursue
Audit and provide feedback	During trial	Whole of practice	Provide general practice with bowel cancer screening data performance reports over the trial to increase engagement with intervention components.
Change physical structure and equipment	Pre-implementation	Whole of practice	Support access and distribution of physical NBCSP test kit to be provided in the general practice.
Change record systems	Pre-implementation	GPs	Enable recording of screening behaviours and subsequent recommendations.
Conduct cyclical small tests of change	During trial	Whole of practice	Implement intervention components using small tests of change (by GP) and refine before implementing practice wide.
Conduct educational outreach visits/meetings	During trial	GPs and practice staff	CTC available via phone or in person to teach participants about intervention components.
Distribute educational materials	During trial	Whole of practice	CTCs to distribute guides to the practice to learn about the intervention components and how to implement them.

Problem solving support	During trial	GPs and practice staff	CTC available via phone or in-person to support practices with challenges implementing the intervention.
Identify and prepare champions	Pre-implementation	GPs and practice staff	Practice trial champion liaising with CTC, supporting intervention activities and overcoming resistance within practice.
Remind clinicians	During trial	GPs and practice staff	CTC reminding participants to use intervention components.

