10.3. Data collection

Data collection, transfer and management will be facilitated by the CTC in conjunction with the PHN (as outlined in the Data Management section below). Table 3 outlines the different methods of data collection for the primary and secondary outcomes.

Table 3 Data collection methods outcomes

Study Outcomes	Time point	Data collection method
Primary Outcomes		
Implementation effectiveness: guideline-appropriate CRC screening recommendation	12-month tracking	Study specific data collection tool integrated into Clinical Information System used in General Practice.
Clinical effectiveness: CRC screening tests completed by patients	12-month tracking	Health analytics/data extraction software used in General Practice.
Secondary Outcomes		
Service outcome: General practice awareness and understanding of guideline-appropriate screening	Pre-, and Post-	Adapted questionnaires (Appendix 4A and 4B)
Implementation outcomes: adoption of in-practice activities and implementation strategies to support CRC screening.	Pre, Mid- and Post-	Adapted questionnaires (Appendix 4C, 4D, 4E and 4F)

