10.3.1. Primary Outcomes

➤ Implementation effectiveness outcome

For the implementation effectiveness primary outcome (*number of guideline-appropriate CRC screening recommendations provided*), a study specific data collection instrument will be used and integrated into Clinical Information Systems (CIS) used in general practice. CISs are used by general practices to facilitate care at an individual patient level. Medical records are stored within the CIS and used by GPs to store information during consultations, such as patient bowel cancer screening history. The National Cancer Screening Register (NCSR) integrates with CIS to allow health providers access to patients' NBCSP participation history from within their CIS.

Medical Director is a CIS used widely across Australia and is already integrated into practices across NSW and WA. Medical Director will enter into an agreement with the University of Sydney under a "Education Support – Master Services Agreement". The agreement will include the development of an electronic prompt which will act as a study specific data collection instrument. Medical Director obtains consent from general practices where their software has been installed to participate in research project. Data will be extracted from the general practice CIS via Medical Director and is de-identified, and no identifiable data leaves the CIS. Medical Director data are managed in accordance with relevant privacy and health records legislation.

➤ *Clinical effectiveness outcome*

For the clinical effectiveness primary outcome of the *number of guideline-appropriate CRC screening tests completed by patients*, de-identified, aggregate patient data will be extracted from CIS. These data will be obtained from the PHN (Health Analytics Software).

PHNs collect data from general practice electronic medical records stored within their CIS through Health Analytics Software tools. The tools used render the data drawn from practice databases unidentifiable, enabling it to be disclosed for research purposes under the Privacy Act 1988 (Privacy Act). PHNs facilitate the licensing of Health Analytics Software to support the extraction, analysis and management of general practice data in the form of population health reports, including bowel cancer screening participation.

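### Register integration, record audits and a change to recording go to the intervention arm, while co-primary B is read from those same practice records, so better recording cannot be told apart from more screening

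*Protocol*

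**What the plan says.** **What is randomised.** In Protocol 10.2.1, Table 1, the clinical system enhancement component includes "clinical audits of patient data to identify under-screened patients and integrate practice CIS with the NCSR". In 10.2.2, Table 2, the row on changing record systems, aimed at GPs and placed before implementation, is there to "Enable recording of screening behaviours and subsequent recommendations". The same section says that the strategies "will be used to support the intervention arm by preparing and supporting the general practices in engaging with the intervention". The synopsis timeline describes the control arm as usual care, monitored by the coordinators.

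**What is measured.** Hypothesis 2 (section 7) and co-primary B (8.1) concern tests that patients complete. Under 10.3.1, for this outcome "de-identified, aggregate patient data will be extracted from CIS", obtained through the Primary Health Network (PHN). Table 3 names the method as "Health analytics/data extraction software used in General Practice". Section 10.3.1 describes the records in the Clinical Information System (CIS) as "used by GPs to store information during consultations, such as patient bowel cancer screening history".

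**Where tests happen.** Section 6.1 says that the programme kit is "mailed to the home of all Australians aged 50-74 years". A kit can therefore be completed without the practice taking part.

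**Independent source.** Table 6 (11.1.2) lists the national programme's screening data with the register as custodian and marks access for the coordinating centre as not provided.

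**The concern.** The outcome is meant to be tests done, but what is counted is tests found in the practice record. A test reaches the count only if it was done and also recorded. The intervention package acts on both steps: it aims to increase screening, and it includes elements that may make records more complete. The control arm is offered nothing by the trial that acts on recording.

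Table 4 adds a second route. It classifies patients by looking back 2 years for iFOBT and 5 years for colonoscopy. An older test entered during the trial can move a patient out of the under-screened column although nobody was newly screened.

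Section 7 tests for a statistically significant increase on this outcome. Section 15 sends the result into a predictive model, cost-effectiveness analyses and a policy recommendation on national scale-up. A recording artefact would travel with it.

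**Working it through.** **Step 1: is there a safeguard elsewhere in the protocol?**
- Baseline audit (10.2): it precedes allocation, so it cannot correct a change in recording that follows allocation.
- Covariates (10.4, 10.4.1): stratification factors, risk category, gender, age and area-level socioeconomic status. None measures completeness of recording.
- Blinding of the statistician (10.6): no help, because the difference would already be in the data.
- Coordinators' dictionary of metrics (11.1.2): not specific to an arm, but it standardises what is extracted, not what was recorded.
- Register counts: not available to the trial team (Table 6).

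Nothing equalises or checks recording by arm. No analysis of these extracts alone could separate the two explanations, so this is a design matter and not one that can be left to an analysis plan.

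**Step 2: how large could it be?** The protocol states no figure to reproduce: no completion rate, capture rate, intra-practice correlation (ICC) or patients per practice. The inputs below are assumptions, except the 50 practices per arm (10.1.2).

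Recorded rate = true rate × capture. With the same true rate in both arms, the recorded ratio is capture (intervention) / capture (control).

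| True rate, both arms | Capture, control v intervention | Recorded | Difference | Ratio |
|---|---|---|---|---|
| 40% | 80% v 85% | 0.40 × 0.80 = 32% v 0.40 × 0.85 = 34% | +2 points | 0.85/0.80 = 1.06 |
| 40% | 70% v 80% | 0.40 × 0.70 = 28% v 0.40 × 0.80 = 32% | +4 points | 0.80/0.70 = 1.14 |
| 40% | 70% v 90% | 0.40 × 0.70 = 28% v 0.40 × 0.90 = 36% | +8 points | 0.90/0.70 = 1.29 |

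For true rates of 30% to 50% and the same capture pairs, the difference runs from 0.30 × 0.05 = 1.5 points to 0.50 × 0.20 = 10 points.

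**Step 3: would it show as a significant result?** Assume 300 eligible patients per practice. Effective number per arm = 50 × 300 / (1 + 299 × ICC): 15,000/6.98 = 2,149 at ICC 0.02; 15,000/15.95 = 940 at 0.05; 15,000/30.9 = 485 at 0.10. The chance of p < 0.05 in favour of the intervention, with no true effect and a 40% true rate, by a normal-approximation test of two proportions, is:

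| Capture | ICC 0.02 | ICC 0.05 | ICC 0.10 |
|---|---|---|---|
| 80% v 85% | 29% | 15% | 10% |
| 70% v 80% | 82% | 47% | 27% |
| 70% v 90% | about 100% | 96% | 76% |

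The nominal chance in that direction is 2.5%.

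**Step 4: what the product formula leaves out.** It treats every newly captured test as guideline-appropriate. Table 4 does not: in average-risk patients, more than one iFOBT in the look-back, or any colonoscopy, counts as not appropriate. In the first row of the Step 2 table, the +2 points would vanish if the fuller records also moved 2 in 100 patients out of the appropriate column. In the last row it would take 8 in 100.

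**The case against.** The strongest reply is that the route from register link to outcome is not documented. Section 10.3.1 says that the link gives providers access to a patient's programme history from within the CIS. That describes viewing, and nothing says it fills the fields that the PHN software extracts. A reader might infer that old register results are imported in the intervention arm; the text does not support that as fact. What remains is that access, audits and a recording change each make it easier for staff to enter a result, and Table 2 names recording of screening behaviours outright.

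That Table 2 row could instead refer to the study-specific instrument for recommendations (co-primary A), which control practices would also need. This is a fair reading. But 10.2.2 assigns the strategies to the intervention arm, and the row names screening behaviours as well as recommendations, so the protocol should say which is meant.

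The gap may also be small. All practices must use Medical Director and an extraction tool (10.1.3). Section 10.2.1 says that the components are available from existing tools, and frames the contrast partly as added support. Some control practices may already have the link. This limits the size but does not remove the problem.

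A reader might also conclude that the bias must favour the intervention. Table 4 prevents that, as Step 4 shows.

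Finally, the trial is called a pilot. That lowers the stakes somewhat, but sections 7 and 15 give this result a confirmatory test and a policy use.

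**Conclusion.** The point holds as a risk that the design creates and does not control. The protocol gives the intervention arm elements that can change how completely tests are recorded, reads co-primary B from those records, and has no independent count or completeness check. A difference on co-primary B could therefore not be attributed to screening rather than recording.

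The documents do not show that capture will differ by arm, or by how much. The direction is probably towards the intervention but is not assured. On assumed values, with no true effect, the false ratio is 1.06 for a 5-point capture gap (80% v 85%) and 1.29 for a 20-point gap (70% v 90%). Both figures rest on equal true completion in the two arms and on every captured test counting as guideline-appropriate.

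**What to change.** 1. **Section 10.3.1:** count a test for co-primary B only if its test date falls within the intervention window (March to August 2024), in both arms and whatever the date of entry. Older tests entered later then do not count as completions. The metric dictionary in 11.1.2 must ask for counts by test date. This does not equalise capture of tests done within the window, and the Table 4 look-back still affects how a test is classified, so items 2 and 3 are needed too.
2. **Table 2:** make the change to recording fields identically in all practices before the baseline audit, and say so.
3. **Register integration:** keep it in the co-designed package, since it may be a real mechanism of effect, but report record completeness by arm at baseline and close-out. One workable form is for each practice to compare a sample of its records with the register view that GPs can already reach (6.1) and release only aggregate counts. If completeness differs by arm, limit the conclusion on co-primary B to recorded tests.
4. **Close-out, conditional:** if integration is shown to fill the extracted fields, enable it in control practices after the intervention period and before the September-October 2024 extraction. Without that evidence, do not rely on it.

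Cost: a protocol amendment, modest coordinator time in control practices, and the loss of older tests from the outcome. The register component of the contrast is unchanged; the recording change ceases to be part of it.

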10.2.2. Implementation strategies

A core component of the CTC's role is to support implementation using these strategies. Evidence-based implementation strategies (listed in Table 2) will be used to support the intervention arm by preparing and supporting the general practices in engaging with the intervention. The strategies have been developed against ERIC refined compilation of strategies (13).

Implementation outcomes, the adoption of in-practice activities and implementation strategies to support CRC screening, are also secondary outcomes of the trial.

Table 2 Implementation strategies

ERIC Strategy (13)	Stage of trial	Target of implementation strategy	Example
Alter incentive/allowance structures	During trial	GPs	Work to incentivise the adoption of intervention components by facilitating Continuing Professional Development points for completion. NB: the CTC will highlight the available opportunity for practices to pursue
Audit and provide feedback	During trial	Whole of practice	Provide general practice with bowel cancer screening data performance reports over the trial to increase engagement with intervention components.
Change physical structure and equipment	Pre-implementation	Whole of practice	Support access and distribution of physical NBCSP test kit to be provided in the general practice.
Change record systems	Pre-implementation	GPs	Enable recording of screening behaviours and subsequent recommendations.
Conduct cyclical small tests of change	During trial	Whole of practice	Implement intervention components using small tests of change (by GP) and refine before implementing practice wide.
Conduct educational outreach visits/meetings	During trial	GPs and practice staff	CTC available via phone or in person to teach participants about intervention components.
Distribute educational materials	During trial	Whole of practice	CTCs to distribute guides to the practice to learn about the intervention components and how to implement them.

Problem solving support	During trial	GPs and practice staff	CTC available via phone or in-person to support practices with challenges implementing the intervention.
Identify and prepare champions	Pre-implementation	GPs and practice staff	Practice trial champion liaising with CTC, supporting intervention activities and overcoming resistance within practice.
Remind clinicians	During trial	GPs and practice staff	CTC reminding participants to use intervention components.
CTC=clinical trial coordinator, GP=general practitioner.			

10.3. Data collection

Data collection, transfer and management will be facilitated by the CTC in conjunction with the PHN (as outlined in the Data Management section below). Table 3 outlines the different methods of data collection for the primary and secondary outcomes.

Table 3 Data collection methods outcomes

Study Outcomes	Time point	Data collection method
Primary Outcomes		
Implementation effectiveness: guideline-appropriate CRC screening recommendation	12-month tracking	Study specific data collection tool integrated into Clinical Information System used in General Practice.
Clinical effectiveness: CRC screening tests completed by patients	12-month tracking	Health analytics/data extraction software used in General Practice.
Secondary Outcomes		
Service outcome: General practice awareness and understanding of guideline-appropriate screening	Pre-, and Post-	Adapted questionnaires (Appendix 4A and 4B)
Implementation outcomes: adoption of in-practice activities and implementation strategies to support CRC screening.	Pre, Mid- and Post-	Adapted questionnaires (Appendix 4C, 4D, 4E and 4F)

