Intervention	
The intervention is a multi-component, co-designed general practice-led intervention designed based on the evidence review and co-design process in a larger project, MAIL, GP & SCALE. The co-design process was completed in April 2023 (University of Sydney HREC 2022/755). The intervention comprises the following components:
 
 1. Decision support aids 2. Electronic point-of-care prompt 3. Clinical system enhancement 4. Education 
The intervention will be provided after an initial six months of usual care and data collection. The 6-month period between recruitment and intervention delivery is being used as a wash out period to ensure best measurement of study effects. The intervention will be supported by the CTC. The CTC will guide and facilitate the implementation strategies identified in the evidence review and through the co-design process.
	
Number of participants	The trial includes up to 100 general practices within the jurisdictions of NSW and WA. There will be 50 practices per jurisdiction, with 25 practices randomly allocated to a control arm and 25 randomly allocated to an intervention arm in each jurisdiction.	
Population	The target population residing within NSW and WA is General Practices, including GPs, practice nurses and practice staff.	
Selection and enrolment	
Inclusion criteria:
 
 • Has at least two full-time equivalent GPs willing to participate in the trial • Nominated Practice Champion who is willing and able to liaise with the Daffodil Centre research team • Uses Medical Director software • Uses Pen CS, Polar or Primary Sense • Available over the trial period October 2023 – October 2024 • Windows 10 or high, i5/i7 16GB processing or willing to upgrade • Has over 1000 active patients and sees minimum of 35 adult patients per day 
Exclusion criteria:
 
 • Shares server with another practice • Uses paper-based medical records • Does not share data with PHN 	

5. List of Study Documents

The following table lists each of the study documents:

Appendix	Document Title	Purpose
Recruitment Templates		
1A	General practice recruitment templates	Will be provided to CTC and used to approach and recruit general practices into the study.
1B	General Practitioner and Practice Staff recruitment templates	Will be provided to CTC and used to approach and recruit GPs and practice staff into the study.

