10.2. Trial design

Following recruitment and informed consent, baseline data audits and practice surveys will be undertaken. After baseline data collection, practices will be allocated to the intervention and control arms. After an initial 6 months of usual care in all sites, the intervention will be delivered, and a mid-trial implementation survey undertaken with the intervention sites. At 12 months, the post-trial audit will be undertaken and post-trial surveys to measure the implementation effectiveness and secondary outcomes.

The 6-month period between recruitment and intervention delivery is being used as a **wash out period**. At recruitment, all practices may be exposed or most susceptible to incidental messaging relating to the NBCSP. The wash out period will ensure that we are best able to study the effects of the intervention. During this 6-month period, we will provide briefing and support to the intervention practices via the CTCs.

The flowchart of study procedures is provided in Figure 1 with the trial timeline outlined in the schedule of events ([see 10.8](#)). The dates displayed in the Figure 1 timeline are indicative and dependent on HREC approval. No activities will commence without HREC approval.

Figure 1. Trial Flowchart

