At or slightly above average risk No FDR or SDR with colorectal cancer One FDR with colorectal cancer diagnosed at 55 years or older One FDR or SDR with colorectal cancer diagnosed at 55 years or older	No iFOBT in previous 2 years if 50 -74 years of age	One iFOBT every 2 years. if 50 -74 years of age as part of the NBCSP	More than one iFOBT in previous 2, OR Any colonoscopy
Moderately increased risk One FDR with colorectal cancer diagnosed under 55 years Two FDR with colorectal cancer diagnosed at any age One FDR and at least two SDR with colorectal cancer diagnosed at any age	No colonoscopy in previous 5 years	One colonoscopy every 5 years. CT colonography may be offered if colonoscopy is contraindicated	More than one colonoscopy in previous 5 years, OR iFOBT if colonoscopy has already been performed
Potentially high risk At least three FDR or SDR with colorectal cancer, with at least one diagnosed under 55 years At least three FDR with colorectal cancer diagnosed at any age	No colonoscopy in previous 5 years	One colonoscopy every 5 years. CT colonography may be offered if colonoscopy is contraindicated	More than one colonoscopy in previous 5 years
FDR = first-degree relative; iFOBT= immunochemical faecal occult blood test; SDR = second-degree relative			

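### The co-primary outcome window is not limited to the exposed period: 12 months of tracking includes about four to six months before the intervention starts

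*Protocol*

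**What the plan says.** Table 3 in Protocol section 10.3 lists the same time point for both co-primary outcomes: "12-month tracking". It gives no start date, no end date and no statement of which part is analysed.

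Section 10.2 describes the sequence: "After an initial 6 months of usual care in all sites, the intervention will be delivered". The synopsis (section 4) dates delivery "March - August 2024" and post-intervention data collection "September - October 2024". Section 10.2 adds: "At 12 months, the post-trial audit will be undertaken". The synopsis explains the delay: "The 6-month period between recruitment and intervention delivery is being used as a wash out period to ensure best measurement of study effects". In those same months, section 10.2 says, "During this 6-month period, we will provide briefing and support to the intervention practices via the CTCs".

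Section 10.3.1 words the clinical co-primary as a count of completed tests. Section 10.4.1 sorts patients into appropriate and not appropriate screeners by Table 4, then gives the models for the clinical outcome. Table 4 looks back two years for the average-risk group ("No iFOBT in previous 2 years if 50 -74 years of age") and five years for colonoscopy in the two higher-risk groups.

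The general models in section 10.4 adjust for the stratification factors. Those in section 10.4.1 start with trial arm alone, then add risk category, gender, age and the practice's socioeconomic index, then an interaction of arm with risk category. None lists a baseline outcome value or a period term.

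**The concern.** The wash-out is meant to sharpen measurement of the effect, yet the only stated time point for the co-primaries is long enough to contain it. If events from the wash-out are counted with those after delivery, and no model term separates them, the contrast between arms is averaged over months in which the intervention had not been delivered. The trial could then miss a real effect. Any estimate it does produce would be too small, and section 15 says the results go into a national effectiveness and cost-effectiveness model.

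The second problem is that the clinical co-primary has two forms. A count of tests in a period and a patient's status at close-out are different quantities, and the look-back makes the status depend far more on time before the intervention.

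**Working it through.** The protocol states no power or sample-size figure that depends on the outcome window, so there is no figure of its own to reproduce. The check is arithmetic on its dates, followed by an illustration.

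**Inputs.** Delivery starts in March 2024 (synopsis; taken as 1 March). The final audit falls in September to October 2024 (synopsis; taken as 1 September to 31 October). The tracking period is 12 months (Table 3). The look-backs are 24 and 60 months (Table 4).

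**Share before delivery.** Share = 1 - (days from 1 March 2024 to audit) / (window length). The days are 184 for an audit on 1 September, 214 on 1 October and 244 on 31 October.

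| Window ending at audit | 1 Sep | 1 Oct | 31 Oct |
|---|---|---|---|
| 12 months (365.25 days) | 50% | 41% | 33% |
| 24 months (730.5 days) | 75% | 71% | 67% |
| 60 months (1826.25 days) | 90% | 88% | 87% |

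Counting forward from the start of tracking gives the same range. From 1 September 2023 to 1 September 2024 it is 182/366 = 50%. From 1 November 2023 to 31 October 2024 it is 121/365 = 33%.

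**Dilution of a count.** Assume a constant event rate and no effect before delivery. With a share f of the window exposed, observed rate ratio = (1 - f) + f x RR.

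- f = 0.5: RR 1.20 gives 0.5 + 0.5 x 1.20 = 1.10; RR 1.30 gives 1.15.
- f = 8/12: RR 1.20 gives 1/3 + (2/3) x 1.20 = 1.13.

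**Loss of information at f = 0.5.** The documents give no intra-practice correlation and no event rate, so only a range can be shown.

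- Standard error the same for both windows (between-practice variation dominates): (ln 1.20 / ln 1.10)^2 = (0.1823/0.0953)^2 = 3.66; for RR 1.30, (ln 1.30 / ln 1.15)^2 = 3.52.
- Event counts dominate the variance: the six-month window has half the events and so about twice the variance. The net loss is 3.66/2 = 1.8; for RR 1.30, 3.52/2 = 1.8.

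**Status reading.** The 67-75% and 87-90% in the table are shares of look-back time. They are not effect sizes; converting them would need the timing of past tests, which the protocol does not give.

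**The case against.** The best defence is that Table 3 is a collection schedule and not an analysis window. The protocol calls the first six months a wash-out, gives measurement of the effect as its purpose, and lists separate baseline and post-intervention clinical audits. A post-delivery or change-from-baseline analysis fits that text, and exact limits are often left to a statistical analysis plan. It stands that the text permits this reading. It does not adopt it: no sentence excludes the wash-out, and the models given have neither a baseline nor a period term. Waiting also carries a risk, because the clinical data arrive as aggregate reports (sections 10.3.1 and 11.1.2). If the date limits are not in the request, a later plan may be unable to separate the periods.

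Several stronger readings are tempting, and the documents do not support them.

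- A reader might infer that most of what is measured predates the intervention. For 12-month counts it is half or less. The larger shares hold only if the clinical co-primary is close-out status, and no look-back is stated for the recommendation outcome.
- For recommendations, the data collection instrument is an electronic prompt still to be developed. The protocol does not show when recording begins, so the dilution there depends on Table 3 being met literally.
- A reader might infer that wash-out data will serve as a contaminated baseline. The protocol never proposes this: section 10.2 puts baseline collection before allocation.
- The support given to intervention practices before March means that the arms are not treated identically in that period. If it has an early effect, the dilution is smaller than calculated, so strict dilution and early exposure cannot both be claimed in full.

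**Conclusion.** The point holds in this form: the protocol does not confine its co-primary outcomes to the period in which the intervention can act, and it leaves open whether the clinical co-primary is a count or a status. Followed literally, 33-50% of the tracked time predates delivery. At 50%, with a constant event rate and no earlier effect, a rate ratio of 1.20 appears as about 1.10, and the loss of information lies between about 1.8-fold and 3.7-fold. The upper figure should not be quoted alone, since it needs an unchanged standard error that the documents cannot confirm.

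Because the arms are randomised and share the pre-intervention time, the distortion is mainly towards no effect. A reader might suspect a bias in favour of the intervention; nothing here supports that.

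**What to change.** 1. Define both co-primaries as counts of events dated from intervention delivery (March 2024) to the post-intervention audit, with the same calendar start and end dates in both arms.
2. Reconcile sections 10.3.1 and 10.4.1 by using Table 4 only to judge whether each test or recommendation in that window is guideline-appropriate.
3. Add the practice-level baseline audit value, collected before the November 2023 allocation, as a covariate for the clinical co-primary. Do the same for recommendations where pre-allocation data exist.
4. Write these date limits into the dictionary of metrics used for extraction (section 11.1.2).
5. Report the 12-month count and close-out Table 4 status as secondary outcomes.

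The denominator should not be narrowed to patients who are not up to date in March 2024. That would drop patients who fall due, or become over-screened, during the intervention, and such a cohort may not be obtainable from aggregate reports.

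The cost is a change to the outcome wording, one covariate and the extraction dates. The downside is fewer events in the shorter window. How much precision that costs depends on the between-practice variation, which is not given.
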